2.8.1.1.2 Liver safety related AEs

Standardized MedDRA Queries (SMQs) are groupings of terms from one or more MedDRA SOCs that relate to a defined medical condition or area of interest. They are intended to aid in case identification.

SMQ Table: The number and percentage of patients experiencing adverse events categorized under the SMQ module drug-related hepatic disorders – comprehensive search (SMQ code 20000006, broad search) and its SMQ sub-modules will be reported.

SMQ-PT Table: The more detailed SMQ-PT table including the respective preferred term frequencies falling under the SMQ drug-related hepatic disorders – comprehensive search (SMQ code 20000006, broad search) and its SMQ sub-modules will be provided.

2.8.1.1.3 Other analyses

For the legal requirements of ClinicalTrials.gov and EudraCT, two required tables on treatment emergent adverse events which are not serious adverse events with an incidence greater than 5% and on treatment emergent serious adverse events and SAE suspected to be related to study treatment will be provided by system organ class and preferred term on the safety set population.

If for a same patient, several consecutive AEs (irrespective of study treatment causality, seriousness and severity) occurred with the same SOC and PT:

- a single occurrence will be counted if there is ≤ 1 day gap between the end date of the preceding AE and the start date of the consecutive AE
- more than one occurrence will be counted if there is > 1 day gap between the end date of the preceding AE and the start date of the consecutive AE

For occurrence, the presence of at least one SAE / SAE suspected to be related to study treatment / non SAE has to be checked in a block e.g., among AE's in a ≤ 1 day gap block, if at least one SAE is occurring, then one occurrence is calculated for that SAE.

The number of deaths resulting from SAEs suspected to be related to study treatment and SAEs irrespective of study treatment relationship will be provided by SOC and PT.

2.8.2 Deaths

All deaths as recorded in the final database (i.e., up to database lock) will be included in the listing.

2.8.3 Laboratory data

Data summaries will be provided in SI units. The summary of laboratory evaluations will be presented for three groups of laboratory tests: Hematology, Chemistry and Urinalysis. On presenting summary statistics, laboratory data will be grouped and displayed in an alphabetical order within the Hematology and Chemistry groups and subgroups. Refer to [Section 5.3.1](#) for subgroup definitions.

Descriptive summary statistics (mean, median, standard deviation, Min and Max) of the change from baseline in the laboratory result to each study visit-window by treatment group will be presented. Change from baseline will only be summarized for patients with both baseline and post baseline values and will be calculated as:

$$\text{change from baseline} = \text{post baseline value} - \text{baseline value}$$

In addition, shift tables will be provided for all parameters to compare a patient's baseline laboratory evaluation relative to the post-baseline values. For the shift tables, the grade level based on CTC grade (as defined by CTCAE as listed in [Section 5.3.3](#)) will be used to evaluate whether a particular laboratory test value was Grade 0, 1, 2, 3, or 4 relative to whether or not the baseline value was Grade 0, 1, 2, 3 or 4. These summaries will be presented by laboratory test and treatment group. Shift table will also be provided for urinalysis results to compare baseline to post-baseline extreme values (negative, +, 2+, 3+, or 4+).

The number and percentage of patients with new or worsening laboratory abnormalities based on CTC grade (as defined by CTCAE as listed in [Section 5.3.3](#)) in each visit-window and at any time post baseline will be presented. Patients with specific laboratory abnormalities (defined by CTC grade 3 and 4) will be listed.

Number of patients with newly occurring liver enzymes abnormalities will be summarized. Newly occurring liver enzymes abnormalities are defined in [Section 5.3.2](#).

Liver function tests will also be presented graphically as matrix plots of each of the parameters (ALT, AST, TBIL, ALP) maximum post-baseline/ULN normalized.

For the shift tables, abnormalities based on CTC grades tables and liver frequency distribution tables, all applicable post-baseline values will be checked against the respective criteria and the rules for handling multiple laboratory assessments within visit windows will not be applied.

For continuous variables databased as <lower limit, these will be imputed as being half of the lower limit.

All above summaries include only data up to and including safety cut off.

2.8.3.1 Serology at screening

Collected data of laboratory serology to determine patient's eligibility includes parameters with respect to hepatitis and HIV viruses. Parameters with respect to hepatitis include 1) anti-hepatitis A virus IgM; 2) hepatitis B surface antigen and anti-hepatitis B core antigen IgM/IgG; 3) anti-hepatitis C virus IgG; 4) anti-hepatitis E virus IgM.

The result of each serology parameter is a categorical value. The number and percentage of patients with values in each of the categories will be provided by treatment group for all above mentioned parameters. Serology test should be performed once at screening. For patients with multiple assessments, the latest result will be used in the summary. Additional serology data with numerical values may be collected but will not be reported.

2.8.3.2 Other special lab results

Other non-routine laboratory data include pregnancy test results, CD19+ B-cell counts (refer to as B-cell counts), total IgG, total IgM, [REDACTED]

The B-cell counts, total IgG, and total IgM, will be summarized using descriptive statistics by treatment group and visit-window.

[REDACTED]

[REDACTED]

Number and percentage of patients meeting the notable low level criteria in IgG or IgM at least once will be provided by treatment group. A notably low IgG level is defined as a level that is 20% below the LLN (i.e. equal to or less than 80% of the LLN) and a notably low IgM level is defined as a level 10% below the LLN (i.e. equal to or less than 90% of the LLN).

2.8.4 Other safety data

2.8.4.1 ECG data

ECG data will be collected at screening/baseline visit and EOS visit. Clinically significant findings from ECG evaluations will be reported as AEs and included in the analysis of AEs. ECG parameters include max heart rate, mean PR duration, mean QT duration, mean QRS duration, and QT corrected using Fridericia's correction formula (all as collected on the ECG CRF). Descriptive statistics of each ECG parameter will be provided by treatment group for baseline and the EOS visits.

The number and percentage of patients meeting the criteria defined in [Table 2-7](#) will be provided for each criterion by treatment group for baseline and the EOS visits.

Table 2-7 Criteria for relevant ECG absolute or change from baseline values

Absolute values criteria:	Changes from baseline criteria:
Heart rate: HR <40 or HR > 120 beats/min	QRS complex : increase > 25% compared to baseline
Pulse rate: PR <110 or PR >200 msec	QTcF > 500 msec and QTcF increase > 60 msec
QRS complex: < 70 msec or > 120 msec	
QTcF < 350 or > 450 msec (males)	
QTcF <360 or > 460 msec (females)	

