6.6.5 ECG

An ECG will be performed at Screening or Baseline and EOS visits. Additional unplanned ECGs may be performed at Investigator's discretion if clinically indicated.

Single 12 lead ECGs are collected. The ECG should be recorded (after 10 min rest in the supine position to ensure a stable reading) according to the local site practice. Clinically significant ECG findings at Baseline must be discussed with the Sponsor before administration of study treatment.

The preferred sequence of cardiovascular data collection during study visits is ECG collection first, followed by vital signs, and blood sampling. The Fridericia QT correction formula (QTcF) should be used for clinical decisions.

The original ECGs on non-heat-sensitive paper/and a certified copy on non-heat sensitive paper), appropriately signed, must be collected and archived at the study site. Each ECG tracing must be labeled with study number, subject number, date and time, and filed in the study site source documents.

Findings and clinically significant abnormalities must be recorded on the relevant section of the CRFs capturing medical history/current medical conditions and AEs.

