2.1.2 Visit windows

2.1.2.1 Visit windows definition

Visit-windows will be used for data summaries by visit/time point. Visit windows define a time period “around” the targeted visit date as defined in the evaluation schedule of the clinical study protocol. Visit-windows are non-overlapping, and defined without gaps between consecutive visit windows. The width of visit windows may vary over the course of the study period.

Baseline assessments are defined in [Section 2.1.1](#) and do not require a visit window.

The purpose of visit windows is to analyze data based on the actual study days (rather than "nominal" visits). E.g., if a patient’s Month 1 visit is delayed; it is possible that the Month 1 data be re-aligned to visit-window Month 2 and be summarized under Month 2.

- For **PK concentration** [REDACTED] nominal visits will be used for summaries by visit/time point. Due to the frequent sampling time points during week 8, conventional mapping to visit-windows are not considered appropriate, thus nominal visits are used in order to capture all data as intended.

-For **safety analyses** all visits (scheduled and unscheduled) will be mapped to visit windows. Safety data from unscheduled visits may be reported separately if applicable.

It is possible that more than one assessment of a patient fall into a particular visit-window. [Section 2.1.2.2](#) deals with the statistical approaches to handle multiple visits in a given visit-window.

Tables displaying summary statistics “by visit” will also use the term *visit-window* as column header; this is to remind the reviewer that multiple assessments of a patient might be summarized. Below tables provide visit-windows definitions for applicable parameters.

Table 2-3 Visit-windows for ADA

Visit-window	Start day	Target Day	End day
Week 4	1	28	42

Week 8	43	56	70
Week 12	71	84	97

Table 2-4 Visit-windows for routine laboratory values and IgG and IgM

Visit-window	Start day	Target Day	End day
Week 4	1	28	56
Week 12	57	84	111

Table 2-6 Visit-windows* for [REDACTED] vital signs data after study drug discontinuation

Visit-window	Start day	Target Day	End day
Last assessment on drug	NA	NA	NA (see above or Section 2.1.1)
Week 12 after LDD	2	84	126
Week 24 after LDD	127	168	210
Week 36 after LDD	211	252	294

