2.1.2.2 Multiple assessments within visit windows

It is possible that multiple assessments of a patient fall into the same visit-window (e.g. due to unscheduled visits). All results (scheduled and unscheduled) will be displayed in applicable listings, but only one value (observed or derived) will be selected for summary statistics by visit-window.

For **quantitative variables**, the assessment closest to the target day will be selected. If more than one assessment is at the same distance to the target day, the later one will be selected. For tables displaying the worst case scenario, such as shift tables or notable abnormalities, all assessments within a visit window will be used to identify the worst (e.g. the maximum or the minimum depending on parameter).

For **qualitative variables**, the worst record is selected; it is noted that in the relevant data subsection, worst case is always well defined.

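### SAP 2.8.4.1 ties the notable-ECG count to baseline and EOS and does not settle how unplanned post-baseline ECGs enter it

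*SAP*

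**What the plan says.** **ECG schedule.** SAP 2.8.4.1 states that "ECG data will be collected at screening/baseline visit and EOS visit". Protocol 6.6.5 gives the same schedule and adds: "Additional unplanned ECGs may be performed at Investigator's discretion if clinically indicated".

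**ECG count.** SAP 2.8.4.1 then says that the number and percentage of patients meeting the Table 2-7 criteria "will be provided for each criterion by treatment group for baseline and the EOS visits". SAP 2.1.1 defines EOS, for an individual patient, as the EOS visit. The ECG section has no any-time post-baseline count.

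**General rules for safety data.** SAP 2.1.2.1 says that for safety analyses "all visits (scheduled and unscheduled) will be mapped to visit windows". It adds an optional provision: "Safety data from unscheduled visits may be reported separately if applicable". For worst-case tables, SAP 2.1.2.2 says: "such as shift tables or notable abnormalities, all assessments within a visit window will be used to identify the worst".

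**Other safety data.** SAP 2.8.3 counts new or worsening laboratory abnormalities "in each visit-window and at any time post baseline will be presented".

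**Other routes for an ECG finding.** SAP 2.8.4.1 sends clinically significant findings to the adverse event analysis, and SAP 2.1 commits to listing all data.

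**The concern.** An ECG taken between first dose and the EOS visit is off-schedule and is done because something prompted it. Such ECGs are more likely than a routine trace to show a notable value. If the Table 2-7 count uses only the baseline and EOS traces, the summary can miss an on-treatment value that meets the plan's own numeric threshold.

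ECG is a named endpoint of the secondary safety objective (SAP Table 1-1). What is at stake is one descriptive safety table. The primary bioequivalence analysis is not affected.

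The text also gives two answers to a practical question. A programmer who follows 2.8.4.1 would use the baseline and EOS visits only. A programmer who follows 2.1.2.1 and 2.1.2.2 would look for a window and take the worst value in it. The two could produce different tables from the same data.

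**Working it through.** The plan gives no figure to reproduce here. The check applies each rule to one record and compares the SAP's sections.

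**1. An illustrative record (assumed values).** QTcF is 420 msec at baseline, 515 msec on an unplanned ECG at Week 5, and 430 msec at EOS. Table 2-7 has a change criterion (above 500 msec with a rise of more than 60 msec) and absolute limits of below 350 or above 450 msec for men and below 360 or above 460 msec for women.

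- Unplanned ECG: 515 > 500 and 515 − 420 = 95 > 60, so the change criterion is met. 515 also exceeds both upper limits.
- EOS: 430 is not above 500, the change is 430 − 420 = 10, and 430 lies inside both sexes' limits. No QTcF criterion is met.
- Baseline: 420 lies inside both sexes' limits.

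**2. Result under each reading.**

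- SAP 2.8.4.1 alone: only 420 and 430 are examined, so the patient is counted under no QTcF criterion.
- SAP 2.1.2.1 with 2.1.2.2: if an ECG window attached to EOS covers Week 5, 515 is the worst value in it and the patient is counted.

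**3. Can the second reading be confirmed?** It needs an ECG window. The readable tables in 2.1.2.1 cover ADA, routine laboratory values with IgG and IgM, and vital signs after study drug discontinuation. Table 2-5 is not readable, so its content is unknown. SAP 2.8.4.1 itself names visits and does not refer to windows.

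**4. Comparison with other safety counts in the SAP.**

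- Laboratory abnormalities (2.8.3): by window and at any time after baseline.
- Notably low IgG or IgM (2.8.3.2): counted if met at least once.
- Suicidality (2.8.5): any time after baseline.
- Notable vital signs (2.8.4.2): not tied to one visit.
- Notable ECG values (2.8.4.1): baseline and EOS only.

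**5. After the EOS visit.** Patients who stay on study drug while waiting for the extension repeat the EOS assessments without the ECG (Protocol Table 6-1, footnote 2). The safety follow-up schedule in Protocol Table 6-2 has no ECG row. An ECG in either period would also be unplanned.

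**6. Size per patient.** Using the planned arm sizes, one uncounted patient is 1/62 = 1.6 percentage points in an abdomen arm and 1/13 = 7.7 points in a thigh arm. The documents give neither the frequency of unplanned ECGs nor an expected rate of Table 2-7 findings, so no total can be derived.

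**The case against.** The strongest reply is that the general rules already cover this. SAP 2.1.2.1 commits to mapping unscheduled safety visits to windows that leave no gaps. EOS is the only scheduled post-baseline ECG visit, so a Week 5 ECG would most naturally map to it, and 2.1.2.2 would then take the worst value. This has real force. A reader might infer from 2.8.4.1 that such values are dropped outright, or that every transient abnormality seen only on an unplanned ECG is lost. The documents do not support that, because the general rules may bring those values in and Table 2-5 cannot be read. What remains is that the specific section and the general rules disagree, and nothing in the readable text says which prevails.

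Second, clinically significant findings reach the adverse event tables and all values are listed. The 515 msec value above would be a strong candidate for adverse event reporting, so the record shows how the rules work and is not a typical loss. This stands and limits the effect. But the adverse event route depends on the investigator's judgement and Table 2-7 on fixed thresholds. A value just past a limit and judged not clinically significant could appear in a listing only, with no percentage by arm.

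Third, a reader might infer that every ECG during the 12 weeks of dosing is unplanned. That is not so: patients who stop study drug early have their EOS visit as soon as possible (Protocol 5.6.2), and that mid-study ECG enters the count. An unplanned ECG that is the last one before first dose would serve as baseline under SAP 2.1.1.

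Fourth, one trace per patient at a fixed visit is more comparable across arms than a worst value over a varying number of ECGs. This is a reason to keep the EOS column, not to omit an any-time count.

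**Conclusion.** The point holds as a conflict in the plan with a limited effect. On its own wording, SAP 2.8.4.1 does not count a threshold-crossing value on an unplanned post-baseline ECG. The general rules could count it, and the visible SAP does not settle which applies.

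The values at risk are those that meet a Table 2-7 criterion, occur on an unplanned post-baseline ECG, are absent at EOS, and are not judged clinically significant. How many there would be cannot be estimated. The figures of 1.6 and 7.7 points describe one patient against planned arm sizes and are not a forecast. It would go too far to say that notable ECG findings are under-counted: that would require knowing both that the literal reading was programmed and that such ECGs occurred. It would also go too far to say that the plan has no ECG window, since Table 2-5 is unreadable.

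This is a minor improvement to a descriptive safety table.

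**What to change.** In SAP 2.8.4.1, keep the baseline and EOS columns of the Table 2-7 summary and add a column for any time post-baseline, covering scheduled and unscheduled ECGs up to the safety cut-off of 100 days after last dose. Use the worst post-baseline value per patient for each criterion. For two-sided criteria such as heart rate, a breach in either direction should count.

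This gives every post-baseline ECG up to the cut-off a defined place in the count and brings ECG into line with the laboratory and suicidality summaries.

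The cost is a sentence of SAP text and one table column, using data already collected. The downside is small: patients with more ECGs have more chances to be counted. The EOS column beside it keeps the like-for-like comparison.

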2.1 Data analysis general information

Novartis statistical and programming team will be performing the final CSR analysis as planned in this document unless otherwise specified. The Statistical Analysis System (SAS) 9.4 and/or R 15.2.1 or higher versions will be used.

Unless otherwise stated, summary tables/figures/listings will be on all patients in the respective analysis sets. Categorical data will be presented as frequencies and percentages. For continuous data, mean, standard deviations, median, 25th and 75th percentiles (optional), minimum and maximum will be presented.

The Week 12 CSR analysis cut-off date will be the Week 12 visit date or EOS date if patients drop out of the study prematurely. All data up to this date will be included in the Week 12 CSR. A complete analysis of the post-treatment safety follow-up will be provided in the Final CSR when all patients have completed Safety FU period.

For analyses of adverse events, only data up to and including the safety cutoff of 100 days (5 x 20 days takes the long half-life of ofatumumab into account) after last administration of study drug or the subject entered the Study G2399 will be considered. Therefore, observations obtained more than 100 days after last administration of study drug will be excluded from the

analyses. Nevertheless, all serious adverse events (SAE) and all deaths, regardless of the safety cut-off will be summarized.

All data (collected or derived) will be listed appropriately.

Table 2-1 provides an overview on all planned reporting.

Table 2-1 Analyses for Week 12 registration vs. Final CSR

	Week 12 registration CSR	Final CSR
PK + immunogenicity	Complete	Complete
Tables + figures of planned safety assessments ¹	Complete up to Week 12 / EOS, no reporting of assessments during safety follow-up	Complete, including all assessments during safety follow-up
Listings of planned safety assessments ²	Complete up to 12 week DBL date	Complete, including all assessments during safety follow-up
Adverse events	Up to and including the safety cutoff of 100 days after last administration of study drug or the subject entered the Study G2399 or 12 week DBL date, whatever comes first	Up to and including the safety cutoff of 100 days after last administration of study drug or the subject entered the Study G2399, whatever comes first

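### SAP Table 2-7 joins QTcF > 500 msec and a QTcF increase > 60 msec in one criterion, so no planned ECG table counts patients with a > 60 msec rise

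*SAP*

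**What the plan says.** Table 2-7 in SAP section 2.8.4.1 has two columns, one for absolute values and one for changes from baseline.

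- The only QTcF entry in the change column is "QTcF > 500 msec and QTcF increase > 60 msec".
- The absolute column has sex-specific QTcF limits: for men "QTcF < 350 or > 450 msec (males", and for women "QTcF <360 or > 460 msec (females".
- Numbers and percentages of patients "will be provided for each criterion by treatment group for baseline and the EOS visits".

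The other ECG output in that section is a summary by visit: "Descriptive statistics of each ECG parameter will be provided by treatment group for baseline and the EOS visits". No summary of change from baseline is named for ECG parameters. Sections 2.8.3 (laboratory data) and 2.8.4.2 (vital signs) do name one for theirs.

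Protocol section 9.5.2 lists change from baseline in ECG evaluations, as well as abnormal values, among the safety variables. ECG is part of the secondary safety endpoint in protocol Table 2-1 and SAP Table 1-1.

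**The concern.** A size-of-change threshold and an absolute threshold answer different questions. The first asks whether a patient's QTcF moved a long way; the second asks whether it reached a high value. When they are joined by a logical and, the row answers neither question alone. A count of zero would mean only that no patient had both features. A reader who sees 60 msec printed in the change column could take it to mean that no patient rose by more than 60 msec, which the row does not show.

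What is at stake is how the ECG safety table is read. No hypothesis test depends on it.

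**Working it through.** **Inputs.** The thresholds (500 and 60 msec jointly; 450 msec upper limit for men, 460 for women) come from SAP Table 2-7. The plan gives no QTcF data and no expected count, so there is no figure to reproduce. The patient values below are assumed for illustration.

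**Step 1: the rise that the joint criterion requires.** Let b be baseline, e the EOS value and d = e − b. The criterion is e > 500 and d > 60. Since e > 500 is the same as d > 500 − b, it becomes d > max(60, 500 − b).

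- b = 360: max(60, 140), so d > 140
- b = 380: max(60, 120), so d > 120
- b = 400: max(60, 100), so d > 100
- b = 420: max(60, 80), so d > 80
- b = 440: max(60, 60), so d > 60
- b = 460: max(60, 40), so d > 60

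The printed 60 msec threshold governs only from a baseline of 440 msec upward. Below that, the 500 msec condition sets the required rise.

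**Step 2: rises above 60 msec that meet no QTcF criterion.** The end value must also stay at or below the sex-specific upper limit. This is possible when b + 60 is below that limit: b < 450 − 60 = 390 for men, and b < 460 − 60 = 400 for women. For a man at 380, it covers rises above 60 and up to 450 − 380 = 70 msec.

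**Step 3: the rules applied to assumed patients.**

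| Patient | Rise (msec) | Absolute row | Joint row | > 60 alone | > 500 alone |
|---|---|---|---|---|---|
| Man, 380 to 445 | 65 | no | no | yes | no |
| Woman, 390 to 455 | 65 | no | no | yes | no |
| Woman, 395 to 470 | 75 | yes | no | yes | no |
| Man, 400 to 495 | 95 | yes | no | yes | no |
| Man, 450 to 505 | 55 | yes | no | no | yes |
| Man, 430 to 505 | 75 | yes | yes | yes | yes |

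The first two patients meet no QTcF criterion in Table 2-7. The next two are counted only as being above the sex-specific limit. The fifth exceeds 500 msec but sits in the same row as any man just above 450. Only the last is counted in the joint row.

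**Step 4: does another planned ECG table supply the count?** The by-visit descriptive statistics describe the group at each visit, and individual changes cannot be recovered from them. The absolute rows are counted separately at baseline and EOS and do not use the change. Neither document has a stand-alone count of rises above 60 msec or of values above 500 msec.

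**Step 5: comparison within the SAP.** In the same change column, QRS has its own stand-alone change criterion (an increase above 25%). For liver tests, section 5.3.2 tabulates single-parameter thresholds beside the joint ones, so the components stay visible. QTcF has only the joint form.

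**The case against.** **The values remain visible elsewhere.** This is the strongest point, and it stands.

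- SAP section 2.1 includes the minimum and maximum in summaries of continuous data. The EOS maximum by group therefore shows whether anyone exceeded 500 msec at that visit; if it is 500 or below, the count is zero.
- The SAP states that "All data (collected or derived) will be listed appropriately".
- On adverse events it states: "Clinically significant findings from ECG evaluations will be reported as AEs and included in the analysis of AEs".

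A reader might infer that marked prolongation would go unreported. The documents do not support that. What is missing is a tabulated count, chiefly of rises above 60 msec, which the EOS maximum cannot show.

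**The word and may be a compressed list of two criteria.** This is possible. Elsewhere in the table the word or only joins the low and high limits of one parameter, as in "HR <40 or HR > 120 beats/min", so its use there settles little. The joint reading is still the more natural one, and a programmer following the cell would code it that way. If two criteria were meant, the cell needs the same edit.

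**Nothing in the documents requires separate rows.** Neither document cites a QT standard, so the joint criterion breaches no stated rule. The case for splitting rests instead on protocol section 9.5.2, which names ECG change from baseline as a safety variable.

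**Two further inferences should not be drawn.** One is that the joint row will be nearly empty: the documents give no QTcF distribution, and separate rows could be just as empty. The other is that the woman going from 395 to 470 looks the same as one stable at 470. She is counted at EOS but not at baseline, whereas the stable patient is counted at both. What the table lacks is the individual shift.

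**Conclusion.** The point holds as a minor gap in safety reporting. On the literal reading of Table 2-7, rises above 60 msec that end at or below 500 msec are not counted as changes. Values above 500 msec with a rise of 60 msec or less are merged into the > 450/460 rows. From baselines below 440 msec, the rise needed to be counted is larger than the printed 60 msec, for example more than 100 msec from 400.

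The conclusion rests on reading and as joint. How many patients would be affected cannot be estimated from the documents.

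The practical weight is small. ECG results are descriptive, all arms receive the same drug and regimen, and protocol section 6.6.5 plans one post-baseline ECG, at EOS. A reader might wonder whether the bioequivalence conclusion is affected. It is not: that analysis uses AUCtau and Cmax only.

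**What to change.** In Table 2-7, replace the single QTcF change entry with two separately counted rows: post-baseline QTcF > 500 msec, and QTcF increase > 60 msec from baseline. Keep the joint criterion as a third row if wanted, labelled as requiring both conditions.

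The data are already collected and the cost is one or two rows in one safety table. The current SAP is dated after database lock, so the change should be recorded as a reporting clarification made after lock.
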